10. STUDY RESPONSIBILITIES

10.1 Investigator Responsibility/Performance

The site principal investigator (PI) agrees to be responsible for implementing and maintaining quality control and quality assurance systems to ensure that all work incidental to this protocol is conducted and data are generated, documented, and reported in compliance with the protocol; accepted standards of Good Clinical Practice (GCP); and all applicable federal, state, and local laws, rules and regulations relating to the conduct of the clinical study.

The site PI will provide current copies of the study protocol to all sub-investigators or other site personnel responsible for study conduct. Additionally, the site PI will provide DCRI with copies of all institutional review board (IRB) or Ethics Committee actions regarding the study.

10.2 Training

The initial training of appropriate clinical site personnel will be the responsibility of the DCRI. The PI is responsible for ensuring that staff conduct the study according to the protocol. To ensure proper administration of study agents, uniform data collection, and protocol compliance, the DCRI will present a formal training session to study site personnel, to include instructions for study procedures, the investigational plan, instructions on data collection, methods for soliciting data from alternative sources, and regulatory requirements.

10.3 Monitoring the Investigational Sites

As part of a concerted effort to follow the study in a detailed and orderly manner in accordance with established principles of GCP and applicable regulations, a study monitor from the DCRI will visit the study sites as appropriate and will maintain frequent telephone and written communication.

Remote monitoring will be used for this study. Site managers will schedule monitoring calls to review enrollment, EDC completion, informed consent and overall study management. During monitoring visits, the monitor will perform a review of inclusion/exclusion criteria, informed consent, HIPAA authorization, as well as safety and efficacy endpoints. Sites may be required to provide at a minimum the informed consent and eligibility requirements for patients to the sponsor or designee via a secure system.

Trends will be monitored and, if warranted, the frequency of onsite monitoring visits may be adjusted at sites. Details will be described in the clinical monitoring plan

On-site monitoring visits may be performed at active investigational sites as needed to assure that the investigator obligations are being fulfilled and all applicable regulations and guidelines are being followed. These visits will be initiated based on the findings of monitoring calls and/or data review. The goal of these on-site visits are to assure the facilities are still acceptable, the protocol and investigational plan are being followed, the IRB or Ethics Committee has been notified of approved protocol changes as required, complete records are being maintained, appropriate reports have been made to the

sponsor or designee and the IRB or Ethics Committee, and the investigator is carrying out all agreed-upon activities.

10.4 Study Documentation

Study documentation includes all electronic case report forms, source documents, monitoring logs and appointment schedules, sponsor-investigator correspondence, and regulatory documents (e.g., protocol and amendments, IRB or EC correspondence and approval, approved and signed patient consent forms, Patient contact forms and medical release forms).

The site PI will prepare and maintain complete and accurate study documentation in compliance with GCP standards and applicable federal, state, and local laws, rules and regulations. For each patient participating in the study at the site, the investigator will promptly complete all eCRFs and such other reports as required by this protocol following completion or termination of the clinical study or as otherwise required pursuant to any agreement with the sponsor.

The site PI acknowledges that, within legal and regulatory restrictions and institutional and ethical considerations, study documentation will be promptly and fully disclosed to the sponsor or designee by the investigator upon request and also shall be made available at the investigator's site upon request for inspection, copying, review, and audit at reasonable times by representatives of the sponsor or responsible government agencies as required by law.

The site PI agrees to promptly take any reasonable steps that are requested by the sponsor or designee as a result of an audit to cure deficiencies in the study documentation and eCRFs.

10.5 Source Documentation

Source documents include all original recordings of observations or notations of clinical activities and all reports and records necessary for the evaluation and reconstruction of the clinical study. Accordingly, source documents include, but are not limited to, laboratory reports, electrocardiogram (ECG) tracings, x-rays, radiologist reports, patient diaries, biopsy reports, ultrasound photographs, patient progress notes, hospital charts, pharmacy records, and any other similar reports or records of any procedure performed in accordance with the protocol. Whenever possible, the original recording of an observation should be retained as the source document; however, a photocopy is acceptable provided that it is a clear, legible, and exact duplication of the original document.

10.6 Protocol Deviations

A protocol deviation is defined as an event where the investigator or site personnel did not conduct the study according to the investigational plan. Site investigators must also follow the policy of the reviewing IRB for reporting such deviations to their reviewing IRB per local policy.

The IRB or Ethics Committee will be informed of all protocol changes by the sponsor or the investigator in accordance with applicable regulations and the IRB or Ethics

Committee's established procedures. No deviations from the protocol of any type will be made without complying with the IRB or Ethics Committee's established procedures. Investigators will maintain documentation of the dates and reasons for each deviation from the protocol.

10.7 Data Transmittal and Record Retention

Required data will be entered in the eCRF at the time of or as soon as possible after the patient call/visit or the availability of test results. The site PI will maintain final eCRFs, worksheets, and all other study-specific documentation (e.g., study file notebooks or source documentation) until notified by the sponsor that records may be destroyed. To avoid error, the investigator will contact the sponsor or designee before the destruction of any records pertaining to the study to ensure they no longer need to be retained. In addition, the sponsor or designee will be contacted if the PI plans to leave the institution so that arrangements can be made for the transfer of records. The site PI takes responsibility for maintaining adequate and accurate source documents of all observations and data generated during this study. Such documentation is subject to inspection by the sponsor or designee as well as by federal, state, and local regulatory agencies.

10.8 Study Closeout

Upon completion of the study (defined as all patients have completed all follow-up visits, all eCRFs are complete, and all queries have been resolved), the sponsor or designee will notify the site of closeout, and a study closeout visit will be performed via telephone. All unused study materials can be destroyed by the site when the study is completed. The sponsor or designee will ensure that the site PI's regulatory files are up-to-date and complete and that any outstanding issues from previous visits have been resolved. Other issues to be reviewed at the closeout visit include discussing retention of study files, possibility of site audits, publication policy, and notifying the IRB of study closure.

10.9 Audit/Inspections

Regulatory authorities from the U.S. or abroad may inspect the site during or after the study at a reasonable time and in a reasonable manner. The site PI should contact the sponsor immediately if contacted regarding an inspection. Site personnel are expected to cooperate with personnel from regulatory agencies (e.g., FDA and Health Canada).

10.10 Publication Policies

Members of the Steering Committee will be primarily responsible for creation, review, and submission of publications and presentations relating to the major aspects of the study and approved ancillary analyses within a timely fashion after completion of the study. Details will be contained in the Publication Plan.

11. ETHICAL CONSIDERATIONS

11.1 Informed Consent

The PI has both ethical and legal responsibility to ensure that each patient being considered for inclusion in this study is given a full explanation of the study. Written informed consent will be obtained from all patients (or, at the discretion of the local IRB, the patient's guardian or legally authorized representative [LAR]) before any study-related procedures are performed or given.

Written informed consent will be documented on an informed consent form (ICF) approved by the local IRB/EC responsible for approval of this protocol. The ICF will conform to the applicable requirements of 45 CFR 46, ICH E6 and institutional requirements for informed consent. The site investigator agrees to obtain approval from DCRI of any ICF intended for use in the study before submission of the ICF for IRB approval.

11.2 Confidentiality of Patients

Patient confidentiality will be maintained throughout the clinical study in a way that ensures that study data can always be tracked back to the source data. Patient information collected in this study will comply with the standards for protection of privacy of individually identifiable health information as promulgated by the U.S. Health Insurance Portability and Accountability Act (HIPAA). All records will be kept confidential, and the patient's name and contact information will not be released for US participants to persons other than the DCRI Call Center. Patient records will not be released to anyone other than DCRI or its designees and responsible regulatory authorities when requested. In all cases, caution will be exercised to assure the data are treated confidentially and that the patient's privacy is guaranteed. The DCRI call center will contact the participants in the US. Canadian sites will contact the participants enrolled in Canada to complete the phone follow up and to collect medical records for CEC. Any records sent from the Canadian sites to DCRI for endpoint review will have PHI redacted prior to providing to DCRI.

11.3 Authorization for Use and Disclosure of Protected Health Information

An authorization for use and disclosure of protected health information (PHI) under the HIPAA Privacy Rule will be obtained from every trial patient before enrollment. The investigator is responsible for obtaining patients' (or their LARs') authorizations and signatures and for explaining the elements of the HIPAA authorization form, if necessary.

The site PI will promptly inform DCRI of any restrictions on the use or disclosure of any patient's PHI. The site investigator will also promptly inform the sponsor of written revocation of any patient's HIPAA authorization.

11.4 Human Subject Protections

11.4.1 Research Subject Selection and Justification of Exclusions

There will be no exclusion from participation in the study on the basis of ethnicity or race. Subjects younger than 18 years of age will be excluded from the study, as the target population is adults.

11.4.2 Risks/Discomforts of Study Participation

This study will evaluate the safety and efficacy of warfarin, apixaban and rivaroxaban in patients at high risk for recurrent VTE. These medications are standard of care for treatment of VTE.

11.5 Institutional Review Board/Ethics Committee Review

The appropriate IRB or Ethics Committee must approve the protocol and informed consent documents, agree to monitor the conduct of the study, and agree to review study progress periodically, at intervals not to exceed 1 year. The investigator will provide DCRI with documentation that the IRB or Ethics Committee has approved the study *before* the study may begin.

In addition, the investigator must provide the following documentation to DCRI:

1. IRB or Ethics Committee annual re-approval of the protocol,
2. IRB or Ethics Committee approval of revisions to the informed consent documents or any amendments to the protocol. The investigator will provide DCRI or designee with documentation of all approvals.

11.6 Steering Committee

The Steering Committee will be the primary decision making body of the study and is responsible for its successful completion. The Steering Committee will be comprised of the study principal investigators, the project leader, and selected other investigators with expertise in venous thromboembolism, anticoagulation, biostatistics, and clinical trials.

11.7 Study Advisory Committee (SAC)

Members of the SAC will include the PI, co-PIs, two patient partners, a patient partner physician leader, researchers, and several professional stakeholders (i.e. payers, industry, purchasers) who will act as consultants to the SAC. The SAC will be responsible for engagement activities to identify patient-oriented outcomes and provide recommendations based on each stakeholder member's interests. They will be instrumental in providing updates on patient recruitment and milestones. Opinions and feedback from the professional stakeholders will reinforce that "real-world" concerns are addressed during the trial and that the results can be utilized by all stakeholder end-users. Members of the SAC will be instrumental in dissemination of the trial results to ensure they can be adopted by their respective end-users. The SAC will report to the Steering Committee any recommendations made from the SAC engagement activities and stakeholders. For example, issues arising during the trial, such as slow recruitment rates, would be reviewed by the SAC for discussion and brainstorming with stakeholders. These recommendations would be brought to the Steering Committee for further consideration and approval before execution of a plan.

11.8 Data and Safety Monitoring Board

A data and safety monitoring board (DSMB) will be appointed for the COVET trial, which will include individuals with pertinent expertise in anticoagulation, clinical trials, and biostatistics. The DSMB will advise the Steering Committee regarding participant reported safety events of interest for current participants.

The composition of the DSMB will be specified in the overall DSMB Charter for the study. It is anticipated that the board will include a (1) chair with both clinical and research expertise in anticoagulant therapy, (2) a senior statistician with prior DSMB experience; and (3) a member of the community. A DSMB Charter for the studies will be developed detailing specific data tables to be provided and procedures to be followed. The DSMB Charter will also describe the overall mission, responsibilities, and meeting schedule of the board. The following outlines the procedures for the DSMB. The DCRI statistical team will be responsible for assuring that the DSMB Charter is developed and approved. The Charter will be distributed to the members of the Study Advisory Committee for their review.

The goal of the DSMB will be to monitor patient safety and to review performance of the protocol. At the conclusion of each DSMB meeting, the DSMB Chair will make a recommendation to the Steering Committee and the Study Advisory Committee about the continuation of the study. Currently, we are planning that the DSMB will meet every six months via teleconference. If safety issues arise, additional conference calls can be requested by the DSMB chairman.

Confidential Interim Data Reports will be prepared regularly by the protocol statistician as specified in the Charter. The report will include recruitment and retention rates, outcomes, and other information as requested by the DSMB Chair. We anticipate that in accordance with customary PCORI practices, there will be both an open and closed session for the DSMB meeting.

11.9 Independent Clinical Events Classification (CEC)

The CEC committee will provide independent central adjudication of bleeds, recurrent VTE, and deaths. The guidelines for the adjudication process will be reported in a separate document, the CEC Charter. The members of this Committee will not participate in the enrollment or treatment of patients in this trial, nor will they participate in the DSMB.

11.10 Role of PCORI as a Funding Source

The Patient-Centered Outcomes Research Institute (PCORI) is an independent, nonprofit organization authorized by Congress in 2010. Its mission is to fund research that will provide patients, their caregivers, and clinicians with the evidence-based information needed to make better-informed healthcare decisions. PCORI is committed to continually seeking input from a broad range of stakeholders to guide its work.

Comparison of **O**ral anticoagulants for extended **V**enous
Thromboembolism
(COVET)

Statistical Analysis Plan
NCT 03196349
July 11, 2018

Prepared by [name]

Duke Clinical Research Institute

Table of contents

1. Background	3
2. Study Design	3
3. Study Objectives	4
4. Analysis Population	4
5. Data Sources	4
6. Endpoints	4
6.1 Primary Endpoints	4
6.1.1 Primary Safety Endpoints	4
6.1.2 Primary Efficacy Endpoint	5
6.1.3 Other Study Endpoints	5
6.2 Secondary Objectives	6
7. Sample Size Justification	6
8. Data Safety Monitoring Board (DSMB)	7
8.1 Interim Analysis	7
9. Statistical Methodology	7
9.1 General Analysis Conventions	7
9.1.1 Statistical significance	7
9.1.2 Assumption checks	7
9.1.3 Descriptive statistics	7
9.1.4 Study Tables and Listings	7
9.1.5 Validation procedures	7
9.1.6 Subgroup analyses	7
9.1.7 Timing of analyses	8
9.1.8 Visit Windows	8
9.2 Analysis of Baseline Data	8
9.3 Analysis of Time to “Response” Data	8
9.3.1 Primary and Secondary Endpoint Analysis	8

1. Background

[figure not shown]
Venous thromboembolism (VTE), including deep vein thrombosis (DVT) and pulmonary embolism (PE), is a common, potentially fatal, yet treatable condition and is the third leading cause of mortality by cardiovascular disease. The standard therapy for patients with VTE is anticoagulation for 3-6 months; the most common oral anticoagulants used are vitamin K antagonists (VKA) and direct oral anticoagulants (DOACs). After completing 3-12 months of anticoagulation, patients, clinicians and policy makers are faced with the crucial decision of whether or not to continue anticoagulation lifelong and which anticoagulant to choose. Vitamin K antagonists were the only oral anticoagulants available for many years and DOACs have expanded the choices now available.

To compare a DOACs (apixaban and rivaroxaban) to VKA (warfarin) for extended anticoagulation for safety and efficacy, we propose a pragmatic clinical trial in which 3000 patients who have confirmed acute symptomatic and unprovoked DVT/PE, have completed initial treatment of oral anticoagulation therapy for 3-12 months and are at high risk for recurrent VTE will be randomly assigned in a 1:1:1 ratio to warfarin, apixaban or rivaroxaban. Maximum follow-up will be 12 months. The primary efficacy endpoint is rate of recurrent VTE. The primary safety endpoint is clinically relevant bleeding and/or clinically relevant non major bleeding.

Further details on the background and significance of this trial can be found in the clinical trial study protocol.

2. Study Design

The COVET study is a multi-center, randomized, open-label study conducted in the United States and Canada of approximately 3000 patients who have confirmed acute symptomatic and unprovoked DVT/PE, have completed initial treatment of oral anticoagulation therapy for 3-12 months and are at high risk for recurrent VTE. Eligible patients who consent to participate in the study will be randomized to warfarin, apixaban, or rivaroxaban (see Figure).

3. Study Objectives

The DCRI statistics group will investigate the following objectives:

Primary Safety Objectives:

- Determine if apixaban is superior to warfarin in the reduction of clinically relevant bleeding.
- Determine if rivaroxaban is superior to warfarin in the reduction of clinically relevant bleeding

Primary Efficacy Objectives:

- Determine if apixaban is non-inferior to warfarin in the prevention of recurrent venous thromboembolism.
- Determine if rivaroxaban is non-inferior to warfarin in the prevention of recurrent venous thromboembolism.

Exploratory Objective:

- An exploratory descriptive comparison of apixaban versus rivaroxaban for the prevention of clinically relevant bleeding and recurrent VTEs as a secondary objective.

4. Analysis Population

All-randomized (Intention To Treat - ITT) – this population includes all randomized participants regardless of the actual treatment received. This population will be used for the primary analysis of the primary safety and efficacy endpoints and a secondary analysis of the primary safety endpoints.

Per protocol population – this population excludes participants who have not started the assigned therapy by the time of the 1 month telephone interview. For time-to-event analyses, participants who stop taking the assigned treatment will be censored after permanently stopping the assigned treatment. This population will be used for the primary analysis of the primary safety endpoints and a secondary analysis of the primary efficacy endpoints.

5. Data Sources

There will be only one data source eClinical Operating System (eCOS), which will include:

- electronic Case Report Form (eCRF) which will complete by sites representatives and DCRI Call Center
- CEC database which will be completed by CEC reviewers.

6. Endpoints

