7. STATISTICAL CONSIDERATIONS

7.1 General Design Issues

COVET is a 3-arm prospective, multi-center, open-label, active comparator, randomized study designed to compare the efficacy and safety of apixaban and rivaroxaban compared with standard warfarin therapy. All potential study endpoints will be reviewed by a central adjudication committee that is blinded to treatment assignment. For participants who withdraw consent for follow-up, all data obtained prior to the time of formal withdrawal will be used in data analyses. The duration of follow up from randomization is expected to be twelve months, and all participants will be expected to remain in study until the 12-month follow-up telephone call regardless of whether they are taking their assigned study medication. Reporting of this prospective, randomized, open-label, blinded endpoint design will follow the CONSORT recommendations (Hansson 1992; Paggio 2012).

The primary efficacy endpoint is rate of recurrent VTEs and the primary safety endpoint is clinically relevant bleeding. Secondary endpoints include components of the primary endpoints, all-cause mortality, and other events of interest. The primary efficacy and safety endpoints will be confirmed by a CEC. Participants will be randomized in a 1:1:1 ratio to warfarin, apixaban, or rivaroxaban. Randomization will be stratified by the anticoagulant used during the screening period. For purposes of randomization, the screening anticoagulants will be classified as either warfarin, apixaban, rivaroxaban, or other. The relative open inclusion criteria, limited exclusions, and simple follow-up structure of COVET are an attempt to be pragmatic (Thorpe 2009).

SAS software version 9.4 or higher will be used for all statistical analyses. P-values less than 0.05 will be considered statistically significant unless otherwise specified. Complete details of all planned analyses will be contained in a separate Statistical Analysis Plan (SAP). The SAP will include the planned tables, listings, and figures. In particular, special attention will be given the participants who do not have complete data.

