7.3 Definition of Analysis Populations

All-randomized (Intention To Treat-ITT) population

This population includes all randomized participants regardless of the actual treatment received. This population will be used for the primary analysis of the primary safety and efficacy endpoints.

Per protocol population

This population excludes participants who have not started the assigned therapy by the time of the 1 month telephone interview. For time-to-event analyses, participants who stop taking the assigned treatment will be censored after permanently stopping the assigned treatment.

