7.5 Data Analyses

Baseline characteristics will be presented using mean (standard deviation) and median (25th, 75th percentiles) for continuous variables and as frequencies (percentages) for categorical variables. No formal comparisons will be computed for baseline variables.

The primary analyses for safety primary endpoint will be based on an un-stratified Cox model adjusting for the two treatment indicators and three stratification indicators. The ascertainment time will be based on the time of the first event or censoring time. Stratification will be based on the anticoagulant used during the screening period. The all-randomized (ITT) analysis dataset will be used for the primary analyses. The treatment effect for each DOAC compared to warfarin will be computed using the estimated hazard ratio and associated 95% confidence intervals. Secondary analyses will be based on a Kaplan-Meier estimates on the all-randomized (ITT) and per-protocol populations.

For the efficacy primary endpoint, the primary analysis will be based on a Kaplan-Meier analysis using the all-randomized (ITT) analysis dataset. The 12-month event rates differences between the DOACs versus warfarin will be based on the difference in the Kaplan-Meier estimates and the one-sided upper 95% confidence interval will be based on a bootstrap estimator. Secondary analyses of the recurrent VTE endpoint will be based on the Cox regression model. Exploratory analyses will directly compare the two DOACs for both safety and efficacy endpoints. Additionally, an exploratory analysis will pool the two DOAC arms and compare those estimates with the warfarin treatment group.

For secondary endpoints, the estimated differences between the DOACs and warfarin treated groups will be based on linear models, logistic regression, and Cox models depending on the endpoint. Efforts will be made to limit the amount of missing data for the key endpoints and adherence measures. When necessary, multiple imputation will be used to account for missing covariate information.

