9.3 Analysis of Time to “Response” Data

9.3.1 Primary and Secondary Endpoint Analysis

The primary analyses for safety primary endpoint will be based on a stratified Cox model. The ascertainment time will be based on the time of the first event or censoring time. Stratification will be based on the anticoagulant used during the screening period. The all-randomized analysis dataset will be used for the primary analyses. The treatment effect for each DOAC compared to warfarin will be computed using the estimated hazard ratio and

associated 95% confidence intervals. Secondary analyses will be based on a Kaplan-Meier estimates on the all-randomized and per-protocol populations.

For the efficacy primary endpoint, the primary analysis will be based on a Kaplan-Meier analysis using the all-randomized analysis dataset. The 12-month event rates differences between the DOACs versus warfarin will be based on the difference in the Kaplan-Meier estimates and the one-sided upper 95% confidence interval will be based on a bootstrap estimator. Secondary analyses of the recurrent VTE endpoint will be based on the Cox regression model. Exploratory analyses will directly compare the two DOACs for both safety and efficacy endpoints. Additionally, an exploratory analysis will pool the two DOAC arms and compare those estimates with the warfarin treatment group.

For secondary endpoints, the estimated differences between the DOACs and warfarin treated groups will be based on linear models, logistic regression, and Cox models depending on the endpoint. Efforts will be made to limit the amount of missing data for the key endpoints and adherence measures. When necessary, multiple imputation will be used to account for missing covariate information.

References

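### SAP Section 4 makes the per-protocol population primary for clinically relevant bleeding, while four other statements in the two documents make the all-randomized population primary

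*SAP*

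**What the plan says.** Five statements assign a population to the primary analysis of clinically relevant bleeding.

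- SAP Section 4, per-protocol paragraph: "This population will be used for the primary analysis of the primary safety endpoints and a secondary analysis of the primary efficacy endpoints".
- SAP Section 4, all-randomized paragraph: this population "will be used for the primary analysis of the primary safety and efficacy endpoints and a secondary analysis of the primary safety endpoints".
- SAP 9.3.1, safety paragraph: "The all-randomized analysis dataset will be used for the primary analyses".
- Protocol 7.3, all-randomized definition: "This population will be used for the primary analysis of the primary safety and efficacy endpoints".
- Protocol 7.5, safety paragraph: "The all-randomized (ITT) analysis dataset will be used for the primary analyses".

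Two further statements give the per-protocol set a secondary role for bleeding. SAP 9.3.1 says "Secondary analyses will be based on a Kaplan-Meier estimates on the all-randomized and per-protocol populations", and Protocol 7.5 says "Secondary analyses will be based on a Kaplan-Meier estimates on the all-randomized (ITT) and per-protocol populations". The per-protocol definition in Protocol 7.3 has the same exclusion and censoring rules as the SAP but no sentence making that set primary for anything. Protocol 7.1 expects participants to "remain in study until the 12-month follow-up telephone call regardless of whether they are taking their assigned study medication".

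**The concern.** The first statement cannot stand with the other four. Read literally, Section 4 either moves the primary bleeding analysis to the per-protocol set or names two primary sets without saying which decides.

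The per-protocol set drops participants who had not started the assigned drug by the 1-month call, and it censors those who stop permanently. Both steps depend on what happens after randomization. Protocol 7.5 itself accepts that randomization does not guarantee the validity of per-protocol comparisons. Adherence is self-reported (Protocol 5.3) in an open-label trial. The schedule also allows attempts at the 1-month call to continue until Month 3, so the cut-off for having started can differ between participants.

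If the conflict is still there when results are known, the choice of deciding population could be made with the answer in view.

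**Working it through.** **Side-by-side reading**

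| Source | Primary for bleeding | Role of per-protocol for bleeding |
|---|---|---|
| SAP 4, per-protocol paragraph | Per-protocol | Primary |
| SAP 4, all-randomized paragraph | All-randomized | not stated |
| SAP 9.3.1 | All-randomized | Secondary (Kaplan-Meier) |
| Protocol 7.3 | All-randomized | not stated |
| Protocol 7.5 | All-randomized | Secondary (Kaplan-Meier), sensitivity |

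The statements in SAP 9.3.1 and Protocol 7.5 stand in the safety paragraphs, so they apply to bleeding. For recurrent VTE all sources agree on all-randomized. The conflict is therefore limited to the safety endpoint.

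**The plan's own power figure**

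Inputs from SAP Section 7: 950 per arm, HR 0.50, two-sided 0.05, warfarin 12-month rate 6.0% or 6.8%. With the DOAC rate taken as half the warfarin rate, events are D = 950 × (p + p/2) and the Schoenfeld power is Φ(√(D/4) × |ln 0.50| − 1.96).

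- 6.0%: D = 950 × 0.090 = 85.5, so Φ(4.623 × 0.693 − 1.96) = Φ(1.24) = 89.3%. Two proportions give 88.4% and Freedman 86.9%. The plan says 88%.
- 6.8%: D = 950 × 0.102 = 96.9, so Φ(4.922 × 0.693 − 1.96) = Φ(1.45) = 92.7%. Two proportions give 92.1% and Freedman 90.7%. The plan says above 90%.

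The stated power reproduces. It does not show which population is primary.

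**Can the choice of set change the verdict? (illustration only)**

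The documents give no stopping rates, so these inputs are assumptions: 3% non-starters and 10%, 20% or 30% stopping over 12 months in both arms, unrelated to bleeding risk. Event times are exponential, the test is a log-rank at two-sided 0.05, and superiority counts only in the DOAC's favour. There were 10,000 replicates per scenario at 950 per arm, 6.0% and HR 0.50. With no stopping, the simulation gives 87.5% power at 6.0% and 91.8% at 6.8%, in line with the plan. The factors 0.833 and 0.193 are 1/1.20 and 1/5.19, from the bleeding table in Protocol 1.3.

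| Bleeding hazard after stopping | Power, all-randomized (%) | Power, per-protocol (%) | Verdicts differ (%) |
|---|---|---|---|
| Unchanged | 88.0 / 88.3 / 87.7 | 85.1 / 82.8 / 80.2 | 5.5 / 8.1 / 11.0 |
| 0.833 of on-drug | 87.7 / 87.4 / 87.0 | 85.4 / 83.7 / 81.1 | 5.1 / 6.9 / 9.4 |
| 0.193 of on-drug | 86.3 / 84.3 / 82.0 | 85.7 / 83.1 / 80.6 | 2.3 / 3.8 / 4.6 |
| Other arm's hazard | 74.6 / 63.4 / 50.2 | 85.2 / 82.8 / 80.9 | 11.2 / 20.1 / 31.0 |

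Entries are for 10 / 20 / 30% stopping. At a warfarin rate of 6.8%, verdicts differ in 2.1% to 30.6% of trials over the same grid.

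A further case gives both arms one common off-drug rate, taken from the placebo rates in that table (4,000 replicates). Verdicts differ in 3.1 / 4.0 / 5.8% of trials at 1.2% and in 4.6 / 6.4 / 9.6% at 2.7%.

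The power ordering reverses between the first and last rows of the table, so the figures do not favour either set. Nor do they show an inflated type I error. With equal on-drug hazards and unequal but uninformative stopping (25% in one arm, 10% in the other), per-protocol declared DOAC superiority in 2.2% to 2.5% of trials. Stopping related to bleeding risk is the more serious worry for a per-protocol analysis. It was not simulated, because nothing in the documents informs it.

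**The case against.** The strongest reply is that the rest of the plan already settles the matter. SAP 9.3.1 is the operative methods section and names the all-randomized set, both protocol sections agree, and the protocol's per-protocol definition lacks the disputed sentence. That makes the intent very likely, and it limits the severity. It does not remove the conflict. Protocol 7.1 leaves complete analysis details to the SAP, and neither document gives a rule of precedence. The SAP is also not a plain copy of the protocol: it specifies a stratified Cox model where Protocol 7.5 specifies an un-stratified one.

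A second point concerns the all-randomized sentence, which also gives that set a secondary role for safety. This can be read as the secondary Kaplan-Meier analysis in 9.3.1, in which case it contradicts nothing. It could also be a remnant of a plan in which per-protocol was primary for safety. The sentence still names all-randomized as primary for safety, so the count stands, but the authors should confirm the meaning.

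Third, the illustration is fragile. The first three rows of the table keep the HR at 0.50 after stopping. The highest disagreement comes only from the full swap of hazards. The 950 per arm may already be net of non-starters, since the plan's 5% allowance includes them. With none removed, the unchanged-hazard row gives 4.0 / 7.0 / 8.4% instead of 5.5 / 8.1 / 11.0%. These criticisms are fair, but the finding rests on the text and not on these figures.

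Finally, Protocol 7.5 plans inverse probability weighting for the per-protocol analysis, and Protocol 6.2 collects drug discontinuation and its reason. Both soften the concern about that set, but neither makes it the primary one.

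**Conclusion.** The contradiction is real and stands in the current text: one sentence makes per-protocol primary for bleeding, and four statements make all-randomized primary. The sentence is wrong as written, not merely short of detail, because following it would change the basis of a primary superiority claim for each DOAC. All-randomized is the likely intention, and 12-month follow-up regardless of treatment fits it.

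The consequence cannot be sized from the documents. Under the assumed stopping patterns the two sets disagree on superiority in roughly 2% to 31% of trials, which shows only that the choice can decide the result. Alpha, sample size and stated power do not change. This should be fixed before database lock.

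**What to change.** In SAP Section 4, replace the last sentence of the per-protocol paragraph with wording such as:

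> *Per-protocol analyses are secondary and supportive for both the primary safety and the primary efficacy endpoints.*

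In the all-randomized paragraph, tie the secondary role for safety to the Kaplan-Meier analysis in Section 9.3.1, once the authors confirm that this is what was meant.

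A minor addition: Protocol 7.5 leaves sensitivity detail to the SAP, and the SAP does not mention the inverse probability weighting. SAP 9.3.1 could cross-refer to it for the supportive per-protocol analysis and note that weights built on 1-month adherence do not address censoring at later stopping.

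The cost is one corrected sentence, one clarified phrase and one cross-reference. No new data, patients, alpha or power calculation is needed.
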